8.3.5 Child-Pugh Score: Required for Arm 2 Part II, Cohort D only

The Child-Pugh score will be assessed at screening only. If any of the hepatic ECI criteria are met, document the Child-Pugh score with each visit until the hepatic ECIs resolve. The Class A score is required for study eligibility. (See Section 10.9 for scoring guidelines.)

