1.3.1 Schedule of Activities for Screening

Table 1 Schedule of Activities for Screening

Study Period:	Screening	Notes
Visit Day:	-28 to -1	
Administrative Procedures		
Informed Consent	X	Documented informed consent must be obtained prior to performing any protocol-specific procedures. Tests performed prior to consent as part of routine clinical management are acceptable if performed within the specified timeframe.
Informed Consent for Future Biomedical Research (FBR) (Optional)	X	Consent for FBR is not required to participate in the study.
Inclusion/Exclusion Criteria	X	
Participant Identification Card	X	Participant identification card to be updated with treatment number at the time of treatment assignment.
Demographics and Medical History	X	
Oncology Disease Status and Prior Oncology Treatment History	X	
Mutational Status / Tumor Genetic Alteration(s)	X	Tumor genetic alteration(s) per standard of care, by history if available, as determined by local testing results.
Prior Medication	X	
Clinical Procedures/Assessments		
Tumor Imaging (CT or MRI as indicated) (RECIST 1.1, and iRECIST Response Assessment)	X	Baseline tumor imaging (CT or MRI as indicated) and/or medical photography of cutaneous lesions should be performed within 28 days prior to C1D1.
Arm 1 only: Medical Photography (cutaneous lesions)	X	Refer to Site Imaging Manual for detailed information.

Study Period:	Screening	Notes
Visit Day:	-28 to -1	
Brain Imaging	X	Participants with previously treated brain metastases must undergo brain imaging within 28 days prior to the first dose of study treatment, with local confirmation that no new or untreated brain metastases are present.
Additional Imaging (PET/CT, bone scan, etc.)	X	May obtain additional scans if clinically indicated. Arm 1: HNSCC Cohort B: Include head and neck CT
Endoscopy	X	Required for Arm 2 Part II, Cohort D only. Participants should undergo screening for esophageal varices, unless such screening has been performed in the past 12 months before first dose of treatment.
Physical Examination	X	A full physical examination should be done at screening.
Child-Pugh Score	X	Required for Arm 2 Part II, Cohort D only. If any of the hepatic ECI criteria are met, document the Child-Pugh score with each visit until the hepatic ECIs resolve. Class A score required.
Height	X	
Weight	X	
Vital Signs	X	Includes temperature, pulse, respiratory rate, and blood pressure.
ECOG Performance Status	X	To be performed within 72 h prior to dosing.

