5.2.2 Arm 2 Part II: Visceral Cohort Expansion

5.2.2.1 Specific Exclusion Criteria for Cohort D: Hepatocellular Carcinoma

18. Has had esophageal or gastric variceal bleeding within the last 6 months. All participants should undergo screening for esophageal varices, unless such screening has been performed in the past 12 months before first dose of treatment. If varices are present, they should be treated according to institutional standards before receiving any study intervention.

19. Has Vp4, inferior vena cava, or cardia involvement from HCC based on imaging.

20. Has had clinically diagnosed hepatic encephalopathy in the 6 months prior to initiation of study intervention. Participants on standing rifaximin or lactulose to control hepatic encephalopathy are not eligible for the study.

Refer to Section 5.2.1 for additional exclusion criteria that apply to all tumor cohorts.

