7 DISCONTINUATION OF STUDY INTERVENTION AND PARTICIPANT WITHDRAWAL

7.1 Discontinuation of Study Intervention

Discontinuation of study intervention does not represent withdrawal from the study.

As certain data on clinical events beyond study intervention discontinuation may be important to the study, they must be collected through the participant's last scheduled follow-up, even if the participant has discontinued study intervention. Therefore, all participants who discontinue study intervention prior to completion of the protocol-specified treatment period will still continue to participate in the study as specified in Section 1.3 and Section 8.11.3.

Participants may discontinue study intervention at any time for any reason or be discontinued from the study intervention at the discretion of the investigator should any untoward effect occur. In addition, a participant may be discontinued from study intervention by the investigator or the Sponsor if study intervention is inappropriate, the study plan is violated, or for administrative and/or other safety reasons. Specific details regarding procedures to be performed at study intervention discontinuation are provided in Section 8.1.8.

A participant must be discontinued from study intervention but continue to be monitored in the study for any of the following reasons:

- The participant or participant's legally acceptable representative requests to discontinue study intervention.
- The participant interrupts study intervention administration for more than 6 consecutive weeks. Participants may continue on study upon consultation with Sponsor.

- The participant has a medical condition or personal circumstance which, in the opinion of the investigator and/or Sponsor, places the participant at unnecessary risk from continued administration of study intervention.
- The participant has a confirmed positive serum pregnancy test.
- Confirmed radiographic disease progression outlined in Section 8.2.3 (exception if the Sponsor approves treatment continuation).
- Unacceptable adverse experiences as described in Section 8.4.
- Progression or recurrence of any malignancy, or any occurrence of another malignancy that requires active treatment.
- Intercurrent illness other than another malignancy as noted above that prevents further administration of treatment.
- Investigator's decision to discontinue treatment.
- Use of prohibited concomitant medications as described in Section 6.5.2.

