- Any study intervention-related toxicity specified as a reason for permanent discontinuation as defined in the guidelines for dose modification due to AEs in Section 6.6.
- Completion of 35 treatments with pembrolizumab.

Note: 35 cycles (approximately 2 years) are calculated from the first dose.

- Side effects and/or concomitant medications required for treatment of HIV and/or its complications that are incompatible with continued study treatment (exceptions are permissible, but should be discussed with the Sponsor)
- Participant has any of the following non-overdose HECIs:
 - ALT $>20 \times$ ULN
 - Child-Pugh score of ≥ 9 points
 - Gastrointestinal bleeding suggestive of portal hypertension (eg, esophageal or gastric varices)
 - New onset of clinically detectable ascites
 - Hepatic encephalopathy

- Recurrence of a severe or life-threatening event, or of any of the laboratory abnormalities listed above, that are presumed to be immune-related

For participants who are discontinued from study intervention, but continue to be monitored in the study, all visits and procedures, as outlined in the SoA, should be completed.

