8.4.7 Events of Clinical Interest

Selected serious and nonserious AEs are also known as ECIs and must be reported to the Sponsor.

Events of clinical interest for this study include:

1. An overdose of Sponsor's product, as defined in Section 8.5.
2. All cohorts except HCC-specific expansion cohorts:
An elevated AST or ALT lab value that is greater than or equal to 3X the upper limit of normal and an elevated total bilirubin lab value that is greater than or equal to 2X the upper limit of normal and, at the same time, an alkaline phosphatase lab value that is less than 2X the upper limit of normal, as determined by way of protocol-specified laboratory testing or unscheduled laboratory testing.*

*Note: These criteria are based upon available regulatory guidance documents. The purpose of the criteria is to specify a threshold of abnormal hepatic tests that may require an additional evaluation for an underlying etiology. The study site guidance for assessment and follow up of these criteria can be found in the Investigator Study File Binder (or equivalent).

3. HCC-specific expansion cohort, Arm 2 Part II:
Hepatic ECIs include any of the following events if the events are considered not due to disease progression or TACE as judged by the investigator. All of these events (if not associated with disease progression under study) will require holding study treatment, notification of the event(s) to the Sponsor within 24 hours after awareness via electronic media or paper.

For dose interval modification, refer to Section 6.6.1 (V937) and 6.6.2 (pembrolizumab). For guidance related to the diagnosis and management of hepatic ECIs, refer to Section 6.6.3.

- ALT:
 - Among participants with Baseline ALT $<2 \times$ ULN: ALT $\geq 5 \times$ ULN
 - Among participants with Baseline ALT $\geq 2 \times$ ULN: ALT $>3 \times$ the Baseline level
 - ALT >500 U/L regardless of baseline level

- Total Bilirubin:
 - Total bilirubin >3.0 mg/dL
- Regardless of laboratory values, hepatic decompensation diagnosed clinically, including:
 - New onset clinically detectable ascites requiring intervention for >3 days
 - Hepatic encephalopathy
 - Gastrointestinal bleeding suggestive of portal hypertension (eg, esophageal or gastric varices)

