10.9 Appendix 9: Child-Pugh Score

The Child-Pugh score is used to assess the prognosis of chronic liver disease, mainly cirrhosis. Although it was originally used to predict mortality during surgery, it is now used to determine the prognosis, as well as the required strength of treatment and the necessity of liver transplantation.

Scoring

The score employs 5 clinical measures of liver disease. Each measure is scored from 1 to 3, with 3 indicating most severe derangement.

Measure	1 point	2 points	3 points
Total bilirubin ¹ (mg/dL)	<2.0	2.0 to 3.0	>3.0
Serum albumin (g/dL)	>3.5	2.8 to 3.5	<2.8
INR ² Or Prothrombin time, prolongation (seconds)	<1.7 <4.0	1.7 to 2.3 4.0-6.0	> 2.3 >6.0
Ascites	None	Mild (easily controlled by medication)	Moderate to Severe (poorly controlled)
Hepatic encephalopathy ³	None	Grade I-II (mild or moderate)	Grade III-IV (severe or coma)

¹In primary sclerosing cholangitis and primary biliary cirrhosis, the bilirubin references are changed to reflect the fact that these diseases feature high conjugated bilirubin levels. The upper limit for 1 point is 68 µmol/L (4 mg/dL) and the upper limit for 2 points is 170 µmol/L (10 mg/dL).

²Different textbooks and publications use different measures. Some older reference works substitute PT prolongation for INR

³Hepatic encephalopathy graded according to West Haven Criteria for Semi-quantitative Grading of Mental Status: *Adapted from: Conn H, Lieberthal M. The hepatic coma syndromes and lactulose. Baltimore: Williams & Wilkins; 1979.*

- Grade I: Trivial lack of awareness; euphoria or anxiety; shortened attention span; impaired performance of addition or subtraction
- Grade II: Lethargy or apathy; minimal disorientation for time or place; subtle personality change; inappropriate behavior

- Grade III: Somnolence to semi-stupor, but responsive to verbal stimuli
Confusion; Gross disorientation
- Grade IV: Coma (unresponsive to verbal or noxious stimuli)

Interpretation

Chronic liver disease is classified into Child-Pugh class A to C, employing the added score from above.

Points	Class	One-year survival	Two-year survival
5–6	A	100%	85%
7–9	B	81%	57%
10–15	C	45%	35%

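### In Cohort D, Child-Pugh 9 or more is a mandatory stop, but after screening the score is required only once a hepatic event has occurred, so some routes to 9 need not be detected

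*Combined protocol and SAP*

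**What the plan says.** Section 7.1 (Discontinuation of Study Intervention) opens its list with "A participant must be discontinued from study intervention but continue to be monitored in the study for any of the following reasons". Under the hepatic items it names "Child-Pugh score of ≥ 9 points" as an entry of its own, alongside ALT above 20 times ULN, portal-hypertensive bleeding, any new-onset detectable ascites, and encephalopathy.

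Section 8.3.5 sets when the score is obtained: "The Child-Pugh score will be assessed at screening only". The note in Table 1 gives the one on-study trigger, which 8.3.5 repeats: "If any of the hepatic ECI criteria are met, document the Child-Pugh score with each visit until the hepatic ECIs resolve". Tables 4 and 5, the treatment and end-of-treatment schedules that apply to Cohort D, contain no Child-Pugh row.

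Section 6.6.3 refers to 8.4.7 for what counts as a hepatic event, and attaches a treatment hold and 24-hour Sponsor notification to it. For the HCC cohort, 8.4.7 lists ALT thresholds, total bilirubin above 3.0 mg/dL, and clinical decompensation: encephalopathy, portal-hypertensive bleeding, and "New onset clinically detectable ascites requiring intervention for >3 days". All of these count only "if the events are considered not due to disease progression or TACE as judged by the investigator". Albumin, INR and the Child-Pugh score are not in the list.

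**The concern.** A stopping rule works only if something in the schedule reveals that it has been met. Here the score is needed to apply the stop, but calculating it is required only after one of a narrower set of events. Calling a score of 9 or more a hepatic event, as 7.1 does, does not help: the score must be known before it can prompt its own assessment.

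At stake is consistent use of the plan's own hepatic stop in participants with HCC. Two investigators with the same laboratory results could act differently, one adding up the score and stopping, the other never adding it up. A score of 9 or more reached in this way also would not start the hold and notification in 6.6.3. No endpoint, sample size or interval estimate is affected.

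**Working it through.** **Inputs.** Appendix 9 scores five measures from 1 to 3 points.
- Bilirubin: 2 points at 2.0 to 3.0 mg/dL, 3 points above 3.0.
- Albumin: 2 points at 2.8 to 3.5 g/dL, 3 points below 2.8.
- INR: 2 points at 1.7 to 2.3, 3 points above 2.3.
- Ascites: 2 points for "Mild (easily controlled by medication".
- Encephalopathy: 1 point if absent.

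Cohort D entry is Class A, 5 to 6 points (criterion 27).

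**Check of the scale.** Minimum 5 × 1 = 5 and maximum 5 × 3 = 15, as in Appendix 9.

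**States that meet no listed 8.4.7 criterion.** Bilirubin at or below 3.0 mg/dL (1 or 2 points), ALT below its thresholds, no encephalopathy, no bleeding, no new ascites. This leaves 2 × 3 × 3 = 18 combinations of bilirubin, albumin and INR points.

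Two ascites states are considered: none (1 point), and mild ascites already present at entry (2 points). The second is possible because the Cohort D exclusions in 5.2.2.1 cover encephalopathy ("Has had clinically diagnosed hepatic encephalopathy in the 6 months prior to initiation of study intervention") but do not list ascites. It is compatible with Class A only when every other measure scores 1: 1 + 1 + 1 + 2 + 1 = 6. New-onset ascites is left out because 7.1 already stops for it. Worsening of existing ascites is left out because the open-ended decompensation list in 8.4.7 could cover it.

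**Formula.** Total = bilirubin + albumin + INR + ascites + encephalopathy (1). A total of 9 or more needs the three laboratory measures to sum to at least 7 without ascites, or at least 6 with mild ascites.

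| Bilirubin, albumin, INR points | Total, no ascites | Total, mild pre-existing ascites |
|---|---|---|
| 1, 3, 3 | 9 | 10 |
| 2, 2, 3 | 9 | 10 |
| 2, 3, 2 | 9 | 10 |
| 2, 3, 3 | 10 | 11 |
| 1, 2, 3 | 8 | 9 |
| 1, 3, 2 | 8 | 9 |
| 2, 1, 3 | 8 | 9 |
| 2, 2, 2 | 8 | 9 |
| 2, 3, 1 | 8 | 9 |

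So 4 of 18 reach 9 without ascites (maximum 10) and 9 of 18 with mild ascites (maximum 11), 13 in all.

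**How far a participant must decline.** Without ascites, from 9 − 6 = 3 to 10 − 5 = 5 points. With mild ascites, from 9 − 6 = 3 to 11 − 6 = 5 points.

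**Role of INR.** In 12 of the 13 the INR is 1.7 or higher; the exception is 2, 3, 1 with mild ascites. If INR is rescored to 1 point, 0 of 4 and 3 of 9 still reach 9, so 10 of the 13 depend on INR points.

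**Overlap with Table 14.** Bilirubin is 2.0 to 3.0 mg/dL in 3 + 6 = 9 of the 13. The documents give no ULN. Assuming 1.0 to 1.3 mg/dL, 1.5 × ULN is 1.5 to 1.95 mg/dL, so with a normal baseline these 9 would fall in the Grade 2 bilirubin band, where pembrolizumab is withheld if the event is judged immune-related. The other 4 would not.

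**The case against.** The strongest reply is that the plan has two tiers. Section 7.1 heads its hepatic items as HECIs and 6.6.3 locates HECIs in 8.4.7. On this reading an 8.4.7 event starts the hold, 8.3.5 then requires the score at each visit, and 7.1 says which outcomes make the stop permanent. ALT above 20 times ULN in 7.1 fits as a higher tier of the ALT thresholds in 8.4.7, and Table 16 uses decompensation to Child-Pugh C only within a hepatic event. The reading is plausible, but no text states it. It also fits imperfectly: the ascites item in 7.1 is broader than the one in 8.4.7, so 7.1 is not simply a subset of 8.4.7 events.

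Second, there are safeguards. Under 8.3.6.1 laboratory results must be judged acceptable before each dose, 8.3.6 has clinically relevant changes recorded as adverse events, and 7.1 allows a stop for unnecessary risk. These stand as mitigation. A reader might infer that hepatic decline in this cohort is unmonitored, and that would be wrong. What is missing is an albumin or INR limit, or any requirement to sum the score.

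Third, a reader might infer that anticoagulated participants enter close to the stop, because Table 8 accepts a therapeutic INR, and that they need an exemption. The entry rules do not support this. INR above 2.3 gives at least 1 + 1 + 3 + 1 + 1 = 7 points, Class B, which criterion 27 excludes. INR of 1.7 to 2.3 gives 1 + 1 + 2 + 1 + 1 = 6 and is admissible only if every other measure scores 1. An anticoagulant-driven stop would need a later INR rise or new anticoagulation, with decline elsewhere. An exemption would also relax a mandatory stop.

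Finally, adding the score to 8.4.7 keeps that section's attribution judgement, so some variation between investigators would remain. That is true, but they would at least be judging a known score.

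**Conclusion.** The point holds as a gap between a mandatory stop and the schedule meant to reveal it. As written, a Cohort D participant can reach Child-Pugh 9 or more through combined albumin, INR and bilirubin decline with no required step that detects it.

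Its size is modest. A reader might take 4 of 18 and 9 of 18 as rates. They are counts of scoring patterns, and the documents give no basis for a frequency. Such cases are probably uncommon: the participant must lose at least 3 points from Class A without meeting an ALT, bilirubin, ascites, encephalopathy or bleeding criterion, and 12 of the 13 routes need INR of 1.7 or more.

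The conclusion assumes that 7.1 applies as worded, without a prior 8.4.7 event as a condition. If the two-tier reading was intended, the text should say so. The amendment summary states that the study is being discontinued, and the documents do not show whether any Cohort D participant remains on treatment. This is worth considering as a safety improvement; it does not threaten the analysis.

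**What to change.** Two changes for Cohort D:

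1. In 8.3.5 and Table 4, derive the Child-Pugh score on Day 1 of each cycle from total bilirubin, albumin, PT/INR and the physical examination (ascites, encephalopathy). State that PT/INR at Cycles 9 and later applies to every Cohort D participant.
2. Add Child-Pugh 9 or more to the HCC list in 8.4.7, under its existing attribution rule, so that it matches 7.1 and triggers the hold and 24-hour notification in 6.6.3.

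Leave the 7.1 stop, the threshold of 9 and the Appendix 9 scoring unchanged, with no exception for anticoagulated participants.

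Cost: protocol wording and one derived eCRF field. Table 4 already marks the chemistry panel, PT/INR and physical examination in every cycle column, and Table 21 includes albumin and total bilirubin in the panel. The PT/INR entry for Cycles 9 and later carries a footnote about participants on anticoagulants and is ambiguous for the others, so the change may mean an added local test for them. The downside is a few more recorded hepatic events and discontinuations, including some driven by an anticoagulant-raised INR that develops after entry. The benefit is limited to any Cohort D participants still on treatment.

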8.3.6 Clinical Safety Laboratory Assessments

Refer to Appendix 2 for the list of clinical laboratory tests to be performed and to the SoA for the timing and frequency.

- The investigator or medically qualified designee (consistent with local requirements) must review the laboratory report, document this review, and record any clinically relevant changes occurring during the study in the AE section of the CRF. The laboratory reports must be filed with the source documents. Clinically significant abnormal laboratory findings are those which are not associated with the underlying disease, unless judged by the investigator to be more severe than expected for the participant's condition.
- All protocol-required laboratory assessments, as defined in Appendix 2, must be conducted in accordance with the laboratory manual and in the SoA.
- If laboratory values from nonprotocol-specified laboratory assessments performed at the institution's local laboratory require a change in study participant management or are considered clinically significant by the investigator (eg, SAE or AE or dose modification), then the results must be recorded in the appropriate CRF (eg, SLAB).
- For any laboratory tests with values considered clinically significantly abnormal during participation in the study or within 30 days after the last dose of study intervention, every attempt should be made to perform repeat assessments until the values return to normal or baseline or if a new baseline is established as determined by the investigator.

8.3.6.1 Laboratory Safety Evaluations (Hematology and Chemistry)

Laboratory tests for hematology and chemistry are specified in Appendix 2.

The maximum amount of blood collected from each participant over the duration of the study will not exceed 950 mL (approximately 650 mL blood will be collected in Year 1 and 300 mL blood in Year 2). See Laboratory Manual for additional details.

Laboratory tests for screening should be performed within 3 days prior to the first dose of study intervention. An exception is hepatitis and thyroid serologies, which may be performed within 28 days prior to first dose. After Cycle 1, predose laboratory safety tests can be conducted up to 72 hours prior to dosing unless otherwise noted on the flow charts.

Laboratory test results must be reviewed by the investigator or qualified designee and found to be acceptable prior to administration of each dose of study intervention. Unresolved abnormal laboratory values that are drug-related AEs should be followed until resolution. Laboratory tests do not need to be repeated after the end of treatment if laboratory results are within normal range.

8.3.7 **Pregnancy Test**

Pregnancy testing ([urine or serum] as required by local regulations) should be conducted according to Section 1.3 (SoA) and at the end of relevant systemic exposure for all arms.

- Pregnancy testing requirements for study inclusion are described in Section 5.1.
- Pregnancy testing (urine or serum) should be conducted at monthly intervals during intervention, according to local regulations or if clinically indicated.
- Pregnancy testing (urine or serum) should be conducted for the time it takes to eliminate systemic exposure after the last dose of study intervention(s) as noted in Section 5.1, ie, 120 days following cessation of pembrolizumab.

Additional serum or urine pregnancy tests may be performed as determined necessary by the investigator to establish the absence of pregnancy at any time during the participant's participation in the study. (See Appendix 7 for country-specific requirements.)

8.4 **Adverse Events, Serious Adverse Events, and Other Reportable Safety Events**

The definitions of an AE or SAE, as well as the method of recording, evaluating, and assessing causality of AE and SAE and the procedures for completing and transmitting AE, SAE, and other reportable safety event reports can be found in Appendix 3.

Adverse events, SAEs, and other reportable safety events will be reported by the participant (or, when appropriate, by a caregiver, surrogate, or the participant's legally authorized representative).

The investigator and any designees are responsible for detecting, documenting, and reporting events that meet the definition of an AE or SAE as well as other reportable safety events. Investigators need to document if an SAE was associated with a medication error, misuse, or abuse. Investigators remain responsible for following up AEs, SAEs, and other reportable safety events for outcome according to Section 8.4.3.

The investigator, who is a qualified physician, will assess events that meet the definition of an AE or SAE as well as other reportable safety events with respect to seriousness, intensity/toxicity and causality.

8.4.1 Time Period and Frequency for Collecting AE, SAE, and Other Reportable Safety Event Information

All AEs, SAEs, and other reportable safety events that occur after the participant provides documented informed consent but before intervention allocation must be reported by the investigator if the participant is receiving placebo run-in or other run-in treatment, if the event cause the participant to be excluded from the study, or is the result of a protocol-specified intervention, including but not limited to washout or discontinuation of usual therapy, diet, or a procedure.

- All AEs from the time of intervention allocation through 30 days following cessation of study intervention must be reported by the investigator.
- All AEs meeting serious criteria, from the time of intervention allocation through 90 days following cessation of study intervention or 30 days following cessation of study intervention if the participant initiates new anticancer therapy, whichever is earlier, must be reported by the investigator.
- All pregnancies and exposure during breastfeeding, from the time of intervention allocation through 120 days following cessation of study intervention, or 30 days following cessation of study intervention if the participant initiates new anticancer therapy must be reported by the investigator.
- Additionally, any SAE brought to the attention of an investigator at any time outside of the time period specified above must be reported immediately to the Sponsor if the event is considered related to study intervention.

Investigators are not obligated to actively seek AEs or SAEs or other reportable safety events in former study participants. However, if the investigator learns of any SAE, including a death, at any time after a participant has been discharged from the study, and the investigator considers the event to be reasonably related to the study intervention or study participation, the investigator must promptly notify the Sponsor.

All initial and follow-up AEs, SAEs, and other reportable safety events will be recorded and reported to the Sponsor or designee within the time frames as indicated in [Table 19](#).

Table 19 Reporting Time Periods and Time Frames for Adverse Events and Other Reportable Safety Events

Type of Event	Reporting Time Period: Consent to Randomization/ Allocation	Reporting Time Period: Randomization/ Allocation through Protocol-specified Follow-up Period	Reporting Time Period: After the Protocol-specified Follow-up Period	Time Frame to Report Event and Follow-up Information to Sponsor:
NSAE	Report if: - due to protocol-specified intervention - causes exclusion - participant is receiving placebo run-in or other run-in treatment	Report all	Not required	Per data entry guidelines
SAE including Cancer and Overdose	Report if: - due to protocol-specified intervention - causes exclusion - participant is receiving placebo run-in or other run-in treatment	Report all	Report if: - drug/vaccine related. (Follow ongoing to outcome)	Within 24 hours of learning of event
Pregnancy/Lactation Exposure	Report if: - participant has been exposed to any protocol-specified intervention (eg, procedure, washout or run-in treatment including placebo run-in)	Report all	Previously reported – Follow to completion/termination; report outcome	Within 24 hours of learning of event
ECI (require regulatory reporting)	Report if: - due to intervention - causes exclusion	Report - potential DILI - require regulatory reporting	Not required	Within 24 hours of learning of event
ECI (do not require regulatory reporting)	Report if: - due to intervention - causes exclusion	Report - non-DILI ECIs and those not requiring regulatory reporting	Not required	Within 5 calendar days of learning of event

DILI=drug-induced liver injury; ECI=event of clinical interest; NSAE=nonserious adverse event; SAE=serious adverse event

